Alaris™ PCA pumps were used for all patients. The PCA profile (i.e. configuration of the light cue operation) for both groups was set up by a nurse in the post-anesthesia care unit (PACU). The starting opioid dose is standardized, and was set up by the PACU nurse. For the control group, the PCA pump was used according to the hospital's standard operating procedures: The PCA emitted a "beep" with every button press, and the status of the green light on the button never changed (i.e., it remained continually lit). For the light group, the PCA pump was configured so that the PCA button only emitted a "beep" when a button press resulted in successful opioid delivery. The green light on the button flashed during opioid delivery, was darkened immediately after delivery and was illuminated at the end of the lockout period, indicating a dose was ready to be delivered. Treatment of side effects was determined by the floor nurse who was not a member of the study team. To ensure consistent messaging, patients and parents in both groups were given scripted instructions regarding PCA use. The patient and guardian were also given a printed copy of the instructions prior to surgery.

PCA monitoring and Pain assessments

Either morphine or hydromorphone (converted to morphine equivalents) was administered using PCA for both groups as prescribed by the anesthesia service. Using morphine equivalents, our standardized PCA orders are as follows: 20 mcg/kg for the PCA dose and basal (if used), 8 minute lockout, and a 120 mcg/kg hourly maximum.

Patients had continuous pulse oximetry. Pain and sedation scores were recorded every 2 hours for the first 24 hours, with a minimum of every 4 hours thereafter. PCA use, including injections (i.e. button presses resulting in delivered doses) and attempts (i.e. button presses during the lockout period), were documented hourly by a nurse who was not a member of the study team. If for some reason the nurse was unable to document the hourly number of

injections and attempts (e.g. busy with another patient), the following hour's data would reflect the previous 2 hours' worth of attempts and injections.

Data collection terminated when the PCA was discontinued, or up to 60 hours post-surgery, whichever came first. The study period was defined as beginning when the patient arrived in the Post-Anesthesia Care Unit (PACU) through Post-Operative Day (POD) 2.

Measures

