All outcomes were collected on post-operative days (PODs) 0-2, with the exception of state anxiety on POD 0, which was collected prior to surgery in the pre-op holding area. The research coordinator administered the STAI once on each POD, and also extracted all other data from the participant's electronic health record (EHR).

Demographics, anthropometrics, and treatment

Demographics (age, sex, race and ethnicity) and anthropometrics (height, weight, and BMI percentile) were extracted from the EHR. Benzodiazepine (lorazepam, diazepam), acetaminophen, ibuprofen, and ketorolac use and intraoperative methadone administration were also extracted from the EHR. These data were collapsed across PODs, and reported as presence/absence. Pre-existing chronic pain was also extracted from the EHR and reported as presence/absence.

Primary Outcome: Patient satisfaction with pain management

The primary outcome was the patient's response to a single question, focused specifically on satisfaction with pain management: "*How satisfied were you with your pain management (was your pain well controlled)?*," with 0 = "very dissatisfied" and 10 = "very satisfied". Participants answered additional questions to rule out factors that could potentially explain between-group similarities or differences in opioid consumption (e.g. Did you

understand how to use the pain pump?). These questions were completed independently by the patient within 24 hours of the end of the study period. Questions were developed by experts in pediatric pain management and were based on the study by Patak et al.¹

Secondary Outcomes

Opioid consumption and opioid-related side-effects

Data on opioid consumption and treatment of related side effects were extracted from the EHR. Total opioid consumed via PCA was calculated from all opioid delivered via the basal rate and via injections, and is reported in mg/kg/hr. Hydromorphone was converted to morphine equivalents by multiplying the total amount of hydromorphone consumed (mg) by 5.²

Data on side effects requiring treatment included nausea/vomiting, pruritus, over sedation (using the Children's Hospital of Wisconsin Sedation Scale,³ and respiratory depression. Treatment was coded as yes/no for each POD.

Pain intensity

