between continuous variables. Comparisons between intervention and control groups and between age groups [children (≤ 12 years) and adolescents (13-17 years)] were conducted using a Mann-Whitney test. Missing data were treated using listwise deletion, and assumed to be missing completely at random. A two-sided p-value <0.05 was used to define what was considered significant.

Multivariable analyses using a mixed model with random time were used to examine the effect of the intervention group and age group on two dependent variables (DV): 1) opioid consumption over time and, 2) injections:attempts ratio over time. The independent covariates (IV) considered were pain scores, methadone use and the interaction between methadone use and intervention group, age group, intervention group, and the interaction between age group and intervention group. A backward model selection procedure was used, with a p-value <0.05 as a criterion to keep the variable in the multivariable model. Based on this criterion, the interaction between intraoperative methadone and intervention group was dropped from the model. The DV opioid consumption was transformed using square root to satisfy model assumptions. The parameters were estimated using Maximum likelihood, and unstructured covariance structure was used for repeated measurements. The mixed model with random effects allows for missing data, under the assumption that data were missing at random. Statistical analyses were calculated using SPSS 24 (IBM SPSS Inc., Chicago, IL) and SAS 9.4 software (SAS Institute Inc., Cary, NC).

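### The injections:attempts ratio has no value when there are no lockout presses, and the plan states no zero rule, time unit or scale for modelling it

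*Combined protocol and SAP*

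**What the plan says.** PCA monitoring and Pain assessments defines the two counts as "injections (i.e. button presses resulting in delivered doses) and attempts (i.e. button presses during the lockout period". They do not overlap: a press counts either as a delivered dose or as a lockout press. Nurses documented them hourly; after a missed hour, the next entry's "data would reflect the previous 2 hours". Follow-up ran to PCA discontinuation "or up to 60 hours post-surgery, whichever came first". Under Measures, "All outcomes were collected on post-operative days (PODs) 0-2". PCA usage says hourly totals were extracted.

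Statistical Analysis then models "two dependent variables (DV): 1) opioid consumption over time and, 2) injections:attempts ratio over time", by maximum likelihood with random time and unstructured covariance. Pain score, methadone use, age group, intervention group and two interactions are candidate covariates. A square-root transformation is given for opioid consumption only. Listwise deletion is stated with data assumed missing completely at random (MCAR), and the mixed model is said to allow for data missing at random (MAR). Nothing says what happens to a record with zero attempts, whether a record is an hour or a POD, or on what scale the ratio is analysed.

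**The concern.** With no lockout press the denominator is zero. Such a record is not missing: both counts are known, and every press delivered a dose. In the light group the button "was illuminated at the end of the lockout period, indicating a dose was ready to be delivered", so periods without wasted presses are what the cue is meant to produce. If software drops them silently, the removed records are those where the cue worked best. If the cue does reduce lockout pressing, more are removed from the light arm. Removal is then determined by the outcome's own value, which neither the MCAR nor the MAR statement describes. If both arms press at the same rate, the loss is equal.

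The second problem is scale. A ratio with a small, variable denominator has a long right tail, and a few patients who rarely press during lockout can dominate a Gaussian model of it. What is at stake is the plan's only adjusted analysis of button use, the behaviour that the light targets.

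**Working it through.** **No figure of the plan's own to reproduce.** The documents give no press rate, SD or power for this ratio. The only inputs taken from them are 60 completed patients per group (Recruitment and Randomization), two-sided 0.05, the count definitions and the 60-hour limit. All rates below are assumed.

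**Unit.** Unstructured covariance has T(T+1)/2 parameters: 3×4/2 = 6 for three PODs, 60×61/2 = 1,830 for 60 hourly records. With 120 patients only the first is workable. Pain, a covariate, is also sparser than hourly: "Pain and sedation scores were recorded every 2 hours for the first 24 hours, with a minimum of every 4 hours thereafter". POD totals are therefore the better-supported reading, but the plan does not say so. It matters: at 2/h and 1/h under a Poisson model, exp(−2) = 14% and exp(−1) = 37% of hourly ratios would be undefined.

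**Undefined POD records.** Take PODs of 12, 24 and 24 h, and patient press rates that follow a gamma distribution with shape k (smaller k means patients differ more). Then P(no attempt) = (1+μ/k)^(−k), where μ is the expected attempts in the record.
- k=1, control (2/h, μ = 24, 48, 48): (1/25 + 1/49 + 1/49)/3 = 2.7%.
- k=1, light (1/h, μ = 12, 24, 24): (1/13 + 1/25 + 1/25)/3 = 5.2%.
- k=0.7: 6.2% against 9.9%. k=2: 0.3% against 1.1%.
- Rarer presses (0.5/h against 0.25/h), k=1: 9.9% against 17.9%.

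**Skew.** With Poisson counts, 20 expected injections and 5 expected attempts, the true ratio is 20/5 = 4.0. The computed ratio averages 5.2 with a coefficient of variation of 0.73. At 20 expected attempts the coefficient is 0.34.

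**Power by simulation.** 60 per arm, three PODs as above, moderately linked counts within patient, undefined ratios dropped. The raw and log ratios use a Gaussian ML model with unstructured covariance; the binomial uses a patient random intercept. The planned covariates are not simulated.

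| Patient variation; lockout presses | Raw ratio | log((inj+0.5)/(att+0.5)) | Random-intercept binomial |
|---|---|---|---|
| Gamma k=0.7; 2/h vs 1/h | 37% | 77% | 78% |
| Gamma k=1; 2/h vs 1/h | 61% | 93% | 93% |
| Gamma k=2; 1.5/h vs 1/h | 63% | 83% | 85% |
| Log-normal SD 1.0; 2/h vs 1/h | 90% | 99% | 99% |
| Log-normal SD 1.5; 2/h vs 1/h | 62% | 79% | 81% |

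At gamma k=5 and 2/h vs 1/h, the raw and log ratios both reach 100%: nothing is lost.

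**Rarity alone.** In a separate simulation (1,500 trials per case, log-normal variation, attempt rate ratio 0.6), patients differed little (log-SD 0.3) and controls made about 5 attempts per POD. The raw ratio had 75% power and the random-intercept binomial 97%. At 20 attempts per POD the figures were 95% and 98%.

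**No true difference.** The raw ratio rejected in 4.8–6.3% of trials with log-normal variation and 4.8–8.0% with gamma variation (500 trials per case). The random-intercept binomial rejected in 4.6–5.7%. A pooled logit with patient-clustered standard errors rejected in about 8–12% at log-normal SD 1.5.

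**The case against.** The strongest reply is that the documents contain no press rates, so the power loss may be negligible. With similar patients and frequent presses it is, and this stands. It does not answer the missing zero rule, which follows from the definitions alone.

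A second reply is that replacing the ratio with a binomial proportion is a preference and changes the estimand. This also largely stands. A reader might infer that a binomial model is clearly better than a repaired ratio. The simulations do not support that: log+0.5 comes within 0 to 2 points of the random-intercept binomial in every row of the table. Nor will any binomial method do. At log-normal SD 1.5 with linked counts, the pooled logit with cluster-robust variance had 57–60% power against 62–78% for the raw ratio, besides rejecting too often under the null.

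Three other readings go too far:
- That the loss arises only when patients differ widely. Rare presses alone can cause it.
- That the raw ratio produces false positives. No clear excess was shown.
- That the analyst did drop zero-attempt records, or that the reported effect is biased by a known amount. The plan is silent on their handling, so this is conditional.

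**Conclusion.** The concern holds as a gap with consequences. As written, the model has a response that is undefined for some fully observed records and badly scaled for others, and the missing-data statements do not cover the records at risk. In the simulated 2/h vs 1/h cases with moderate linkage and wide patient variation, moving to log+0.5 raises power by 9 points (log-normal SD 1.0: 90% to 99%) to 40 points (gamma k=0.7: 37% to 77%). These figures depend on assumed rates, patient variation and linkage, and on undefined records being dropped; confidence in the size is medium at best.

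The consequence is lost power for a secondary outcome. The primary outcome, satisfaction with pain management, does not use these counts and is unaffected. The same cannot be said outright for the Mann-Whitney comparisons: the plan does not list their variables, and if the ratio is among them, undefined values would meet the same problem under listwise deletion. The change should be made, but it does not undermine the trial's main comparison.

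**What to change.** In Statistical Analysis:
- State POD as the time unit for this model. This also absorbs most entries that cover two hours.
- Replace the raw ratio with log((injections+0.5)/(attempts+0.5)), keeping the planned mixed model and covariates.
- Equivalent option: a binomial (logit) mixed model with a patient random effect on injections out of (injections + attempts). If chosen, restate the estimand as the odds that a press delivers a dose.
- Do not rely on a pooled logit or GEE with cluster-robust variance alone.
- Report by arm the number of POD records with no attempts.

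The cost is a few sentences and a changed response variable or procedure call, using counts already extracted. Effects would be on a log-ratio or odds-ratio scale, less direct to read than a ratio. The 0.5 is a convention that matters most when counts are small; a record with no press of either kind would receive log(0.5/0.5) = 0, so the number of these should be given as well.

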Investigating the effects of cuing medication availability on patient-controlled analgesia pump usage in pediatric patients: Results of a randomized controlled trial

NCT02456909

Date of Document: March 30, 2015

Study Protocol and Statistical Analysis Plan

Materials and Methods

This single-center, prospective, RCT was conducted at a large children's hospital in the Midwest. The study was approved by the hospital Institutional Review Board, and was registered at www.clinicaltrials.gov (ID: NCT02456909) by the principal investigators prior to study enrollment. Enrollment was April 2015 – August 2017.

Participants

Potential participants between the ages of 7 – 17 years, undergoing an orthopedic, abdominal or thoracic surgery for which PCA is routinely prescribed for post-operative pain management, were identified from the hospital surgery schedule. Eligible patients were opioid naïve, and patients and at least one parent were able to read and speak English. Exclusion criteria included 1) prior experience with PCA, 2) cognitive delay precluding independent use of the PCA button, or 3) pre-operative use of a daily anxiolytic or antidepressant medication.

Procedures

Recruitment and Randomization

Patients were approached immediately prior to surgery. After informed consent and assent were obtained, participants were randomized into either the control group or the experimental “light” group and were stratified by gender and surgical procedure (orthopedic, abdominal, or thoracic) in blocks of 4. The randomization scheme was created by a statistician on the research team using Windows version 6.0 of “rand.exe” (<http://block-stratified-randomization.software.informer.com>). Participants were enrolled by the clinical research coordinator, who used the scheme to assign participants to groups after consent. Recruitment continued until each group included 60 completed participants (defined as having completed at least 24 hours of PCA use and completed assessment of the primary outcome). Carefusion

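### Both mixed models list pain scores, a post-randomization secondary outcome, as a covariate, so the group coefficient need not be the light's total effect

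*Combined protocol and SAP*

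**What the plan says.** The Statistical Analysis section gives the models' purpose: "Multivariable analyses using a mixed model with random time were used to examine the effect of the intervention group and age group", for two dependent variables, opioid consumption over time and the injections:attempts ratio over time. One candidate list serves both: "The independent covariates (IV) considered were pain scores, methadone use and the interaction between methadone use and intervention group", followed by "age group, intervention group, and the interaction between age group and intervention group".

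Terms were then selected: "A backward model selection procedure was used, with a p-value <0.05 as a criterion to keep the variable in the multivariable model". One result of that selection is given: "Based on this criterion, the interaction between intraoperative methadone and intervention group was dropped from the model". The section does not list the final terms of either model, describes no version without pain scores, and names no direct-effect or mediation question.

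The timing is set out elsewhere:

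- **Recruitment and Randomization:** "Patients were approached immediately prior to surgery. After informed consent and assent were obtained, participants were randomized". The PACU nurse then configures the assigned cue profile.
- **Pain intensity (under Secondary Outcomes):** the scores run from PACU departure until the PCA stops or POD 2 ends.

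Separately, the plan describes Mann-Whitney tests without covariates: "Comparisons between intervention and control groups and between age groups". It does not say which outcomes they cover.

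**The concern.** Randomization makes the two groups comparable at baseline. A covariate measured later, under the assigned cue, can itself be changed by the cue. Adjusting for it takes out any part of the light's effect that runs through pain. It can also bring in confounding by anything that drives both pain and PCA use. The coefficient then describes use at comparable pain, not the difference the light makes.

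The text presents the models as examining the intervention's effect and gives no such qualification. They are the only longitudinal estimates of that effect listed for the two outcomes, and a reader cannot tell which question they answer.

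**Working it through.** The plan states no figure on this point, so there is none to reproduce. The check has a textual part and an illustrative part.

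**1. Order of events.** Randomization comes before surgery, the cue is configured in the PACU, and pain scores begin on leaving the PACU. So no analysed pain score is a baseline value. Intraoperative methadone is different: it is given before the cue is set up, so the cue cannot affect it.

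**2. Was pain kept?** Six candidate terms are named and one is reported as dropped. Retention of pain is implied, not stated.

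**3. Algebra (one summary per patient).** Let T be the total effect of the light on the outcome, d its effect on pain, and b the within-group slope of the outcome on pain. The pain-adjusted group coefficient is

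T − b × d.

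It equals T if b = 0 or d = 0. The documents give neither value, so size and direction are unknown.

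**4. Size under assumed b and d.** Inputs: 60 per group (from the plan), two-sided 0.05 (from the plan), unit SDs, T = 0. The residual SD is √(1 − b²) and the SE is residual SD × √(2/60). The rejection rate comes from a noncentral t with noncentrality b × d / SE.

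| b | d | Bias (SD) | SE | Noncentrality | Rejection rate |
|---|---|---|---|---|---|
| 0.3 | 0.1 | 0.03 | 0.174 | 0.17 | 5.3% |
| 0.3 | 0.3 | 0.09 | 0.174 | 0.52 | 8.1% |
| 0.5 | 0.1 | 0.05 | 0.158 | 0.32 | 6.1% |
| 0.5 | 0.3 | 0.15 | 0.158 | 0.95 | 15.6% |

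Simulation with the p < 0.05 rule applied to pain (6,000 runs per cell) agrees: 4.9 to 5.9%, 7.3 to 8.0%, 5.7 to 5.8% and 14.0 to 15.7% in the same order, against 4.5 to 5.4% unadjusted. Pain was kept in 91 to 92% of runs at correlation 0.3 and in 100% at 0.5.

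**5. Which route could make d non-zero?** Starting dose is standardized and the groups differ only in cues, so the obvious route to pain is opioid intake. If that is the only route, no effect on opioid use means d = 0, and the opioid model's null is protected. A non-zero d with zero effect on opioid use needs another route, for example anxiety. The trial measures anxiety, but no document shows that the light changes it.

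**6. Repeated-measures version, closer to the plan.** All parameters are assumed: 3 PODs, 60 per group, maximum likelihood with unstructured covariance, 4,000 runs. Pain raises same-day opioid use, opioid lowers next-day pain (−0.3), and a shared patient factor affects both.

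| Scenario | b about 0.27 | b about 0.46 |
|---|---|---|
| Intake only, no effect: rejection without / with pain | 5.4% / 6.0% | 5.2% / 5.3% |
| Intake only, real effect: total / adjusted (SD) | −0.481 / −0.507 | −0.454 / −0.508 |
| Other route, zero total effect, d = ±0.1: rejection with pain | 5.9–6.0% | 7.8–8.2% |
| Other route, zero total effect, d = ±0.3: rejection with pain | 9.7–10.2% | 19.4–19.5% |

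Without pain, rejection in the other-route scenarios is 5.3 to 6.4%. The real-effect row fits the algebra with d = +0.10 and +0.12:

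- −0.481 − 0.27 × 0.10 = −0.508
- −0.454 − 0.46 × 0.12 = −0.509

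The overstatement is 0.507/0.481 = 1.05 and 0.508/0.454 = 1.12.

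**The case against.** The strongest reply is that the harm depends on two unknowns: whether pain was kept and whether the light changes pain. The sentence on the dropped term refers to a single model although there are two, so it may not be a full account. On the most plausible route, opioid intake, the false-positive rate stays near nominal and a real effect shifts by only 5 to 12%, with no change of sign. The larger rates need d = ±0.3 by another route, which no document supports. Use at comparable pain is also a reasonable secondary question for patient-controlled dosing, adjustment gains precision, and the Mann-Whitney comparisons carry no pain adjustment.

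Much of this stands:

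- The bias is possible, not demonstrated.
- At b about 0.27 and d = ±0.1, the rates with pain lie inside the range seen without it. The Monte Carlo standard error at 4,000 runs is about 0.4 percentage points, so no inflation is shown there.
- The simulation was written for opioid use and assumes a daily time unit. The injections:attempts ratio was not simulated separately.

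It does not remove the point. The intake-only reassurance covers the opioid model and does not carry over to the ratio, which the cue could change directly through attempts. Pain is measured as an outcome, so the analysis should not depend on the light's effect on it being zero. The Mann-Whitney tests, whose outcomes are not listed, do not repair the mixed-model coefficient. A pain-adjusted analysis is legitimate if labelled, and this one is not.

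**Conclusion.** The concern holds, conditionally. Pain scores are post-randomization, are a secondary outcome, and are candidates in both models meant to examine the light's effect. If they were kept, as the text implies, the group coefficient need not be the total effect.

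The likely consequence for opioid use is modest: a somewhat overstated real effect if opioid intake is the only route. A materially raised false-positive rate, roughly 8 to 19% across the two sets of assumptions, requires d of about ±0.3 by another route, and that is an assumption without support in the documents. For the ratio, the size is not established. The primary outcome, satisfaction with pain management, is untouched, as is any covariate-free comparison. The point should be fixed, because the text does not let a reader tell which effect is being reported; it does not overturn the trial.

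**What to change.** - For both dependent variables, report a mixed model without pain scores as the main estimate of the light's effect. Intraoperative methadone may stay.
- Keep the intervention term whatever its p-value. Under p < 0.05 selection with a true 0.3 SD effect and 60 per group, it survives in 37% of runs, and the surviving estimates average about 0.48 SD.
- Take the overall effect from a model without the age-by-group interaction, or average it over age groups, and report the interaction separately. With that term in and an assumed 50:50 age split, the group coefficient refers to one age group, its SE is √2 = 1.41 times larger, and power for 0.5 SD is 48%, not 78%.
- Analyse pain as its own outcome, and label any pain-adjusted model exploratory, as use at comparable pain.
- List the final terms of each model, say whether pain was kept, and state which outcomes the Mann-Whitney tests cover.

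The cost is a re-run of two models and a few lines of text; no new data are needed. Some precision is lost if the light does not affect pain. In the one-summary calculation, power for 0.5 SD is about 78% without pain, against 81% with it at a pain–outcome correlation of 0.3 and 88% at 0.5.

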Pain scores: Pain scores were recorded from the time patients left the PACU until discontinuation of the PCA or through POD 2 (whichever came first) and were extracted from the EHR. Pain was assessed using the age appropriate, hospital approved pain scale. Children either used a 0-10 (0 = no pain, 10 = worst pain possible) numeric rating scale, or the 0-10 Faces Pain Scale-Revised [10].

PCA usage

The total number of hourly injections and attempts were extracted from the EHR.

State Anxiety

The Spielberger State-Trait Anxiety Inventory for Children (STAIC), state version, is a well-validated 20 item questionnaire used to assess anxiety about a current situation or impending event⁴. Each question begins with the stem “I feel...” and ends with 3 choices (e.g., “very calm,” “calm,” “not calm”). Respondents are instructed to consider “*how you feel right now.*” A total score is computed from a sum of the items, with scores ranging from 0 – 60. The STAIC was administered by the research coordinator once before surgery (POD 0) and once per day on POD 1 and POD 2. Elevated state anxiety was based on T-scores and was defined as ≥ 1 standard deviation above the mean.⁵

Power Analysis:

An *a priori* sample size calculation was based on the primary outcome. Rahman et al. examined patient satisfaction with pain relief for those randomized to pain management with PCA vs. intravenous boluses of analgesia titrated to patient comfort levels.⁶ Based on a 1-5 scale (1 = excellent, 5 = disappointing), the average pain relief rating for patients in the PCA group was significantly better at 2.0 (± 0.37) than the rating for patients in the control group at 3.0 (± 0.24). With a power of 80%, a type I error rate (alpha) of 0.05, and a two-tailed t test, 60 patients would have been needed in each group to detect a difference of at least 0.16 SD between the light and control groups.

Statistical Analysis

Modified intent-to-treat analyses included all randomized participants, with the exception of those who did not receive the allocated intervention, as shown in Figure 1. Means and standard deviations or median and interquartile range (IQR) when data were skewed, were used for continuous data, and categorical items were described using frequency statistics. A Chi-square test or a Fisher’s exact test was used to explore the relations between categorical variables, and bivariate correlations (Pearson correlation test) were used to explore correlations

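### The mixed models for outcomes over time list no fixed time effect and no intervention-by-time term, so they cannot show whether the cue's effect changes over POD 0-2

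*Combined protocol and SAP*

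**What the plan says.** The Statistical Analysis section introduces the models thus: "Multivariable analyses using a mixed model with random time were used to examine the effect of the intervention group and age group". The dependent variables are "1) opioid consumption over time and, 2) injections:attempts ratio over time". The candidate terms are given as "The independent covariates (IV) considered were pain scores, methadone use and the interaction between methadone use and intervention group, age group, intervention group", followed by "and the interaction between age group and intervention group". Backward selection at p<0.05 is applied, and one removal is reported: "Based on this criterion, the interaction between intraoperative methadone and intervention group was dropped from the model". On estimation: "The parameters were estimated using Maximum likelihood, and unstructured covariance structure was used for repeated measurements".

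The data are longitudinal. Injections and attempts are charted every hour (PCA monitoring and Pain assessments), and outcomes cover PODs 0-2 (Measures). Pain is a repeated measure too: "Pain scores were recorded from the time patients left the PACU until discontinuation of the PCA or through POD 2". The section does not say whether random time is a slope for each patient or a factor shared by all patients, nor whether its unit is the hour or the POD.

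**The concern.** A random time effect describes how patients vary around a mean, and an unstructured covariance describes dependence between repeated values. Neither puts a trend into the mean or compares the arms' trends. A light that signals dose availability could plausibly matter most while patients are learning the pump and less later, or the reverse. A model with a single arm term returns a blend of such effects and gives no sign that they differ.

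A second, conditional issue concerns pain. If pain and opioid use both change systematically after surgery and time is not in the mean model, the pain coefficient can pick up part of the shared trend.

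**Working it through.** **1. Inventory of terms.** Pain, methadone, methadone × intervention, age group, intervention and age group × intervention are listed. Fixed time, intervention × time and age group × time are not. The only removal reported is methadone × intervention, so no time term is shown as considered and then dropped.

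**2. What the arm term estimates.** Write G for arm, A for age group, M for methadone, P for pain, and b for a patient-level random slope with mean zero. After the reported removal, the mean model is

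E(Y at time t) = β0 + β1·P + β2·M + β3·A + β4·G + β5·A·G.

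The arm difference is β4 + β5·A, which contains no t. With fixed effects τ(t) and θ(t)·G added, it becomes β4 + β5·A + θ(t). Only then can it vary by day.

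**3. What a changing effect would look like.** The documents give no values, so these are assumptions: 60 per arm (the recruitment target in Recruitment and Randomization), three PODs, within-patient correlation 0.5-0.6, opioid use and pain each falling 0.5 SD per POD, half of patients off PCA by POD 2, two-sided 5%. Two separately coded simulations (3,000 and 1,000 trials) gave the power below. The joint test asks whether the arms differ on any POD.

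| Assumed cue effect, POD 0/1/2 (SD) | Single arm term | Joint test of POD-specific differences |
|---|---|---|
| 0.6 / 0.3 / 0 | 70% | 86-88% |
| 0.6 / 0 / -0.3 | 31-33% | 98% |
| 0.5 / 0.5 / 0.5 | 87-88% | 75-78% |

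In the first row the single term averages about 0.40 SD, whereas the simple mean is (0.6 + 0.3 + 0)/3 = 0.30 SD. Fewer patients contribute on POD 2, so the average leans towards the early days. In a separate set-up (N = 120, three time points), an arm difference in slope of 0.4 per day that averages to zero was detected in 99% of trials with the interaction term. The arm-only model flagged an arm effect in 15% and has no term for the slope difference.

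**4. The pain coefficient.** Let pain fall along a slope δ, and let use have its own slope γ beyond what pain explains. In the simplest case (exchangeable correlation, pain coefficient estimated within patients), omitting time makes it tend to

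β1 + γ·δ·V / (W + δ²·V),

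where V is the variance of the time points and W the within-patient variance of pain about its trend. The bias is zero if γ or δ is zero, and upward if both fall. Other covariance structures change its size. Simulated means:

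| Assumptions | True | Without fixed time | With fixed time |
|---|---|---|---|
| Set-up of step 3; use falling 0.3 to 0.8 SD per POD | 0.20 | 0.31-0.40 (0.37 at 0.5 SD) | 0.20 |
| 3 points, pain -0.7/day, use -0.5/day | 0.30 | 0.51 | 0.30 |
| Same, use -1.0/day | 0.30 | 0.55-0.56 | 0.30 |
| 12 points, use -0.5 or -1.0/day (only 15 simulations) | 0.30 | about 0.35 | 0.29-0.30 |
| Use has no own trend, or pain has none | 0.30 | 0.30 | 0.30 |

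The figures without fixed time use an unstructured covariance or a patient-level random slope. If random time is instead a factor common to all patients (approximated by fitting time as a factor), the coefficient is 0.29-0.30. A further check with three points and no dropout gave 0.35-0.42 for a truth of 0.20. The ratio to the truth therefore runs from 1 to 0.42/0.20 = 2.1.

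**5. The average arm contrast.** In the runs with truth 0.30, mean arm estimates with and without fixed time differed by at most about 0.02, against standard errors of 0.147-0.153 at three time points. With assumed POD 2 retention of 60% versus 40% and no cue effect, the spurious arm difference was 0.02-0.045 SD.

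**The case against.** The strongest reply is that the stated aim is only to "examine the effect of the intervention group and age group on two dependent variables (DV): 1) opioid consumption over time", and a period-averaged contrast is a legitimate estimand for a repeatedly measured outcome. A changing cue effect is not a stated hypothesis, and the scenarios that favour the richer model are chosen rather than taken from the documents. With a constant effect, the single term is the more powerful test. All of this stands. It is why the averaged contrast should remain the main one, and why this is an improvement to secondary analyses rather than a failure to test something promised.

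Three stronger readings are tempting and are not supported:

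- *The pain coefficient is biased.* That depends on the unstated form and unit of random time, and on trends that the documents do not report. For the injections:attempts ratio no trend is given and none was simulated. Pain is in any case an adjustment variable, not the target.
- *The arm comparison is invalid because the time trend leaks into it.* Step 5 shows that the effect on the average contrast is negligible.
- *Time was left out of the fitted model.* The list may be incomplete reporting of a model that did contain fixed time. The documents do not say so, and the text can be judged only as written.

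**Conclusion.** The point holds in limited form. On the text alone, both models lack a fixed time effect and an intervention-by-time term, and so cannot show whether the cue's effect changes across POD 0-2. This needs no assumption beyond taking the list of terms as complete.

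The cost in power depends on an assumed pattern. It is large if the effect reverses, moderate if it fades, and absent if it is constant. Distortion of the pain coefficient is a possibility, not a finding: none to about double, on assumed values.

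Only secondary outcomes are involved. The primary outcome is a single satisfaction rating and is unaffected.

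**What to change.** 1. State the form of random time (patient-level slope or shared factor) and its unit (hour or POD), and whether any fixed time term was fitted.
2. In both models add time (POD 0, 1, 2 as a categorical factor, or the unit actually analysed) and time × intervention as fixed effects exempt from backward selection. Let the random and repeated-measures parts model covariance only.
3. Keep the period-averaged arm difference as the main contrast and define its weights over PODs. Once the interaction is in the model, the coefficient for arm alone refers to the reference day, so the average has to be requested explicitly.
4. Report the joint time × intervention test and the arm difference on each POD with 95% CIs as supportive results, without multiplicity-adjusted claims.

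Cost: with three PODs, 2 parameters for time and 2 for the interaction, so 4 per model; more with a finer unit. There are some extra comparisons. If the effect is constant, the joint test of POD-specific differences has less power than the averaged term (75-78% versus 87-88% in the illustration), which is why the averaged contrast is kept. No new data are needed. Because the section already reports a selection result, terms added now should be labelled as added afterwards.
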